## **12.5 Reporting and Exclusions**

### **12.5.1 Evaluation of Toxicity.**

All patients will be evaluable for toxicity from the time of their first treatment with vorinostat.

### **12.5.2 Evaluation of Response.**

All patients included in the study must be assessed for response to treatment, even if there are major protocol treatment deviations or if they are ineligible. Each patient will be assigned one of the following categories: 1) complete response, 2) partial response, 3) stable disease, 4) progressive disease, 5) early death from malignant disease, 6) early death from toxicity, 7) early death because of other cause, or 9) unknown (not assessable, insufficient data). [Note: By arbitrary convention, category 9 usually designates the “unknown” status of any type of data in a clinical database.]

All of the patients who met the eligibility criteria (with the possible exception of those who received no study medication) should be included in the main analysis of the response rate. Patients in response categories 4-9 should be considered as failing to respond to treatment (disease progression). Thus, an incorrect treatment schedule or drug administration does not

result in exclusion from the analysis of the response rate. Precise definitions for categories 4-9 will be protocol specific.

All conclusions should be based on all eligible patients. Sub-analyses may then be performed on the basis of a subset of patients, excluding those for whom major protocol deviations have been identified (e.g., early death due to other reasons, early discontinuation of treatment, major protocol violations, etc.). However, these sub-analyses may not serve as the basis for drawing conclusions concerning treatment efficacy, and the reasons for excluding patients from the analysis should be clearly reported. The 95% confidence intervals should also be provided.

**APPENDIX A**  
***Performance Status Criteria***

| ECOG Performance Status Scale |   | Karnofsky Performance Scale |  |
|--------------------------------------|---|------------------------------------|--|
| Grade                         | Descriptions   | Percent                     | Description   |
| 0                                    | Normal activity. Fully active, able to carry on all pre-disease performance without restriction.  | 100                                | Normal, no complaints, no evidence of disease.                                 |
|                                      |   | 90                                 | Able to carry on normal activity; minor signs or symptoms of disease.          |
| 1                                    | Symptoms, but ambulatory. Restricted in physically strenuous activity, but ambulatory and able to carry out work of a light or sedentary nature (e.g., light housework, office work). | 80                                 | Normal activity with effort; some signs or symptoms of disease.                |
|                                      |   | 70                                 | Cares for self, unable to carry on normal activity or to do active work.       |
| 2                                    | In bed <50% of the time. Ambulatory and capable of all self-care, but unable to carry out any work activities. Up and about more than 50% of waking hours.                            | 60                                 | Requires occasional assistance, but is able to care for most of his/her needs. |
|                                      |   | 50                                 | Requires considerable assistance and frequent medical care.                    |
| 3                                    | In bed >50% of the time. Capable of only limited self-care, confined to bed or chair more than 50% of waking hours.   | 40                                 | Disabled, requires special care and assistance.                                |
|                                      |   | 30                                 | Severely disabled, hospitalization indicated. Death not imminent.              |
| 4                                    | 100% bedridden. Completely disabled. Cannot carry on any self-care. Totally confined to bed or chair.   | 20                                 | Very sick, hospitalization indicated. Death not imminent.                      |
|                                      |   | 10                                 | Moribund, fatal processes progressing rapidly.                                 |
| 5                                    | Dead.   | 0                                  | Dead.  |

## **APPENDIX B**

### **PET Imaging Acquisition Parameters and Image Data Analysis**

Additional information for PET Imaging Acquisition Parameters and Analysis are available on the ACRIN web site at ([www.acrin.org/6678\\_protocol.aspx](http://www.acrin.org/6678_protocol.aspx)).(76)

#### **Acquisition and Analysis of FDG-PET/CT Scans**

FDG-PET/CT scans will be performed according to the guidelines for NCI-sponsored studies as recently published by Shankar et al. (77).

#### **1. Participant Preparation**

Participants must fast for a minimum of 4 hours prior to the injection of FDG for the PET scan. However, they will be encouraged to drink water to ensure adequate hydration.

- Upon arrival at the PET facility, the participant's weight and height will be measured and recorded. Serum glucose should be measured to determine that the blood glucose concentration is within the normal range.
- If the serum glucose concentration is found to be greater than 150 mg/dL, the study should be rescheduled. The referring oncologist or the primary physician of the patient will be contacted to optimize blood glucose control.
- The participant should be placed in a comfortable position, either supine or semi-recumbent. A large-bore intravenous line (21-gauge or greater) should be placed in an arm or hand vein. The room should be kept warm to avoid shivering and temperature effects that may increase muscular or fat uptake. The participant should move as little as possible and should not talk more than necessary in the first 30 min following FDG injection.
- Prior to positioning the participant on the PET scanner the participant should be asked to urinate.

#### **2. Injection of [F] Fluorodeoxyglucose (FDG)**

- The dose of FDG to be administered should be 10 to 20 millicuries (mCi), adjusted according to weight as suggested by the scanner manufacturer.
- FDG will be synthesized and prepared in accordance with USP compendial standards.
- The exact time of calibration of the dose should be recorded and the exact time of injection noted to permit correction of the administered dose for radioactive decay. In addition, the dose remaining in the tubing or syringe, or that was spilled during injection should be recorded. The injection should be performed through an intravenous catheter.

#### **3. FDG-PET/CT Imaging**

- PET scanning must begin  $60 \pm 10$  minutes after FDG injection. The time between injection and the start of the PET scanning for the second and third scans should be matched as closely as possible to that for the first scan (less than 10 min difference in uptake times).
- Participants will generally be positioned in the PET/CT scanner with their arms raised above the head. If participants cannot tolerate this position for the duration of the PET/CT study, a different participant positioning may be chosen. However, arms should be positioned in the same way at the baseline and the follow-up studies.
- A low-dose CT scan will be acquired for attenuation correction and anatomical localization of findings in the PET scan.
- The acquisition parameter for the low-dose CT scan for attenuation correction should be: kV = 120-140; effective mAs = 30-120 (patient dependent); gantry rotation time  $\leq 0.8$  sec; maximum reconstructed width = 3-5 mm without overlap; standard reconstruction algorithm, minimum reconstruction diameter = outer arm to outer arm; and without iodinated contrast (78).
- The axial field of view of the CT scan for attenuation correction will range from the mid thighs to the base of the skull. Arm positioning will be the same as for the PET scan, typically above the head.
- The CT scan will be performed during "shallow breathing" as described previously. No respiratory gating will be applied.
- After the CT scan, a PET scan covering the same axial field of view will be performed. This scan will start at the mid thighs. The number of bed positions and the acquisition time per bed position will be scanner specific. Typical parameters are 6 bed positions and an acquisition of 2-5 min per bed position.

#### **4. Image Reconstruction**

- The PET data will be corrected for dead time, scatter, randoms and attenuation using standard algorithms provided by the scanner manufacturers.
- Image reconstruction will be performed.

#### **5. Image Analysis**

- Activity concentrations in the attenuation-corrected PET images will be converted to standardized uptake values (SUVs) by dividing the activity concentrations by the decay-corrected injected dose and multiplying with the body weight of the participant.
- A circular region of interest (ROI) with a diameter of 0.75 to 1.5 cm will be centered at the site of maximum FDG uptake within this lesion. ROIs of the same size will be placed in the slices immediately above and below, at the same transverse location.

- The average SUV within the volume encompassed by these three ROIs will be determined and recorded. This approach for definition of ROIs has been successfully used for assessment of tumor response in patients with advanced NSCLC .
- In most patients the primary tumor will show the highest FDG uptake. However, in a small subgroup of participants the primary tumor may be small (< 2cm) and show only low FDG uptake in PET or it may have been resected. In this case, the metastatic lesion with the highest FDG uptake will be used for analysis.
- For quality control purposes, a large circular ROI (diameter  $\geq$  5 cm) will be placed in normal liver tissue. The mean SUV in this ROI will be recorded.
- In the case of multiple liver metastases, it may not be feasible to place one large ROI in normal liver tissues. In this case, several small ROIs, including the same number of pixels as one 5-cm ROI, may be placed in normal liver tissue. FDG uptake within these lesions will be averaged and used for further analysis.
- If the mean SUV within the liver changes by more than 1.0 between two scans, the SUV calculation will be checked for errors. Specifically, the scanner cross calibration, the decay correction of the injected activity, and the participant's body weight will be checked (see checklist below for details)

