### **Definition of a Metabolic Response in FDG-PET**

Based on the reproducibility of the FDG-signal in untreated tumors, relative changes of approximately 20% are very unlikely to be due to measurement errors or spontaneous fluctuations of tumor metabolic activity (72,73). These data establish the minimal effect of treatment on tumor metabolic activity that can be assessed by FDG-PET. However, a measurable change in metabolic activity does not necessarily imply that treatment has a beneficial effect for the patient. A recent study evaluated the prognostic implications of a measurable change in tumor glucose utilization in patients with advanced NSCLC, who were treated with palliative platinum-based chemotherapy. A "metabolic response" in PET was prospectively defined as decrease of the SUV of the primary tumor by at least 20%. A total of 57 patients were included in the study and 28 tumors showed a metabolic response after the first chemotherapy cycle. Median progression-free survival of metabolic nonresponders was only 1.8 months versus 5.9 months for metabolic responders. Median overall survival of metabolic responders was 8.4 months and only 5.0 months for metabolic nonresponders (65). The sensitivity and specificity of a metabolic response for prediction of best response according to RECIST criteria were 95% and 74%, respectively.

These data indicate that a measurable change in tumor FDG uptake after the first cycle of chemotherapy is associated with a palliative effect of therapy. These data and the data on the test-retest reproducibility of FDG-PET suggest that a 20% decrease in tumor FDG uptake may be

used to define a metabolic response in patients with NSCLC. However, we will use slightly stricter criteria for a metabolic response in the present study and define a metabolic response as a decrease of tumor FDG uptake by 25%. The rationale for this definition is that the test/retest reproducibility of FDG-PET in a multicenter trial may be lower than previously reported in single-center studies. Therefore, a 20% threshold may not be robust enough for a multicenter trial. Defining a metabolic response as a 25% decrease of tumor FDG uptake makes this study also consistent with previous recommendations by the EORTC (74).

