- 4) Profile the genomes of each cell population using oligonucleotide CGH arrays. This will confirm the identification of tumor populations in each sample and provide genomic landmarks

for NGS analysis.

5) Perform whole exome analysis of the sorted tumor population and matching germ line sample for each of the patients. The combined aCGH and exome data will be mined to identify genes and pathways that are targeted by select somatic events in each of the patient subsets

6) To assess stable disease duration (SDD).

7) To assess the association between response to vorinostat treatment and HR23B on tumor paraffin blocks.

Exploratory Objective 1 concerns the potential association of PET/CT response (magnitude of decrease in SUV after 1 treatment cycle) with clinical response by RECIST 1.1 criteria. Percent change in SUV ( $\Delta$ SUV) is a continuous variable, whereas objective response is a categorical (typically, binary) variable. First, we will use receiver operator characteristic (ROC) curve analysis to determine the optimal cutoff in the distribution of  $\Delta$ SUV, in relationship to objective response (yes/no). That will allow us to define “PET response”. We will also compare the descriptive statistics of the  $\Delta$ SUV distribution in the RECIST responders vs non-responders. At Stage 1 (n=12), the association of  $\Delta$ SUV with subsequent best tumor response will be explored in a simple 2 x 2 contingency table, with point and 90% CI estimates of objective response rates among the patients with vs. without PET response. Descriptively only, we can then examine the point and CI estimates to see if there is a hint of any association. At Stage 2 (n=29), we would repeat the same descriptive, exploratory investigation, and then determine what, if any, additional statistical analysis might be appropriate. For example, that might involve exact logistic regression to model the log-odds of later objective response as a function of only one predictor: early PET response (yes/no). This exact logistic modeling investigation would still be viewed as exploratory only, but would yield a point and 90% CI estimate of the odds ratio for response.

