## 6. Image Interpretation

- Describe the location of the primary tumor and of metastatic lesions if present.
- Measure and record the maximum SUV in the primary tumor and most active metastatic lesion.
- If the diameter of the primary tumor is less than 2 cm or the primary tumor demonstrates only low FDG uptake, measure the maximum SUV of the lesion with the highest FDG uptake.
- Measure and record the mean SUV in the liver as described in [Section 5](#) above.

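### Appendix B does not hold lesion, ROI diameter or SUV type fixed between PET scans, and its liver check misses a 25% scale error unless baseline liver SUV exceeds 4.0

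*Combined protocol and SAP*

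**What the plan says.** Appendix B, 5. Image Analysis, sets the ROI rule: "A circular region of interest (ROI) with a diameter of 0.75 to 1.5 cm will be centered at the site of maximum FDG uptake". Size matching is then required within a scan: "ROIs of the same size will be placed in the slices immediately above and below, at the same transverse location". The SUV averaged over those three ROIs is recorded.

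Appendix B, 6. Image Interpretation, asks for a different quantity: "Measure and record the maximum SUV in the primary tumor and most active metastatic lesion".

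The quality check in 5. Image Analysis reads: "If the mean SUV within the liver changes by more than 1.0 between two scans, the SUV calculation will be checked for errors".

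Section 2.3 says the trial will "define a metabolic response as a decrease of tumor FDG uptake by 25" per cent. It relies on reproducibility data by which "relative changes of approximately 20% are very unlikely to be due to measurement errors", and it raises the threshold from 20% to 25% because reproducibility may be lower across several centres. Section 12.4 instead treats percent change in SUV as continuous: "First, we will use receiver operator characteristic (ROC) curve analysis to determine the optimal cutoff in the distribution of" that change, which then defines PET response for both the RECIST and the PFS analyses. Section 12.4 does not say whether SUV means the three-ROI mean or the maximum.

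**The concern.** A percent change between scans is interpretable only if the same thing is measured the same way each time. Appendix B does control some items between scans: uptake time must agree to within 10 minutes, and arm position must be the same. ROI diameter and lesion are not on that list. A larger ROI takes in more of the lesion edge and lowers the mean, so two readers following the text can obtain different changes from the same images.

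The liver check is meant to catch errors of scale (scanner cross-calibration, decay correction, body weight). Such errors move liver and tumour by the same percentage, whereas the trigger is an absolute SUV difference. What is at stake is the change-in-SUV variable behind exploratory objectives 1 and 2, in at most 12 patients at Stage 1 or 29 at Stage 2.

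**Working it through.** The 25% threshold, the 1.0 trigger and the 0.75-1.5 cm range are stated without derivation, so there is no plan figure to reproduce.

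**Inputs from the documents.** ROI diameter 7.5 to 15 mm and liver trigger 1.0 (Appendix B, 5); response threshold 25% and test-retest limit about 20% (Section 2.3).

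**Assumptions, not in the documents.** Uniform spherical lesion; Gaussian PET resolution (FWHM) 5-7 mm; tumour-to-background contrast 5:1 or 3:1; three slices 4 mm apart; normal-liver SUV 1.5-3.0.

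**1. ROI diameter, tumour unchanged.** The ROI area can vary by (15/7.5)² = 4-fold. Apparent change = (three-slice mean at 15 mm) / (three-slice mean at 7.5 mm) - 1. Where a cell shows a range, it is the spread between separate runs of the model.

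| Lesion | 5 mm, 5:1 | 7 mm, 5:1 | 6 mm, 3:1 |
|---|---|---|---|
| 1.0 cm | -33 to -34% | -24 to -25% | -20 to -22% |
| 1.5 cm | -23% | -21 to -22% | -18% |
| 2.0 cm | -7 to -8% | -11% | -8% |
| 3.0 cm | 0 | -0.5 to -1% | 0 |

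In the reverse order a fall d becomes a rise of 1/(1 - d) - 1. For example, 20% becomes 1/0.80 - 1 = +25%.

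**2. Cross-check with a closed form.** For a Gaussian hot spot, the mean over a disc of radius R is (1 - exp(-x))/x, with x = R²/(2σ²) and σ = FWHM/2.355. At FWHM 15 mm and no background, σ = 6.37 mm.

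- R = 3.75 mm: x = 0.173, mean 0.918 of peak.
- R = 7.5 mm: x = 0.693, mean 0.721 of peak.
- Ratio 0.721/0.918 = 0.786, a fall of 21%. The factor for the outer slices cancels when background is zero.

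With background at 0 / 20 / 40% of peak, the falls are 39 / 28 / 19% at 10 mm, 21 / 16 / 12% at 15 mm, 13 / 10 / 8% at 20 mm and 6 / 5 / 4% at 30 mm. ROI size alone reaches 25% only below about 13.6 mm (no background) or 11.0 mm (20%), and not at 40% for the sizes modelled (10-40 mm).

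**3. ROI change combined with a scale error.** For a 1.5 cm lesion with a 21% ROI artefact, 0.79 × (1 - e) = 0.75 gives e = 1 - 0.75/0.79 = 5%.

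**4. Liver check.** A follow-up scale error e changes liver SUV by e × L, where L is the baseline liver SUV. It is flagged only if e × L > 1.0.

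- e = 25%: flagged only if L > 1.0/0.25 = 4.0.
- L = 1.5: a 25% error moves the liver by 0.375; the check needs e > 1.0/1.5 = 67%.
- L = 3.0: a 25% error moves the liver by 0.75; the check needs e > 1.0/3.0 = 33%.
- If the baseline scan is instead inflated by one third (also an apparent 25% fall, since 1/(4/3) = 0.75), the change is L/3, flagged only if true L > 3.0.

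**5. Metric and lesion, side by side.** Image Analysis uses a mean and leaves the primary if it is under 2 cm *and* of low uptake, or resected. Image Interpretation uses a maximum and leaves the primary if it is under 2 cm *or* of low uptake. A primary of 3 cm with low uptake is kept by the first rule and replaced by the second. Neither says whether the choice is made once, at baseline.

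**6. After the fix.** With one diameter and one lesion, an unchanged tumour gives a ratio of 1, so the ROI artefact is 0. With a relative tolerance of 20%, a 25% scale fall is flagged whatever the value of L.

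**The case against.** The strongest reply is that this is a minor matter in an optional, funding-dependent substudy analysed descriptively. That stands and limits the weight of the point. Other replies also have force:

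- **Size.** The table uses the extreme swing from smallest to largest ROI. The 10 mm minimum in Section 3.1.2 is a RECIST rule, not a rule for choosing the PET lesion, so 1.0 cm lesions are not shown to be typical. A reader might infer that 25% metabolic responses would commonly appear with no tumour change. The documents do not support that: ROI size alone gets there only at about 1 cm, and no frequency can be given.
- **Threshold.** Section 12.4 sets the cut-off by ROC analysis, so 25% is not the operative rule there. This changes the mechanism but does not remove the problem: a distorted percent change also distorts an ROC cut-off and the Cox estimate.
- **Mixing metrics.** Nothing tells sites to use the mean at one scan and the maximum at another. The defect is an unnamed analysis quantity and two unreconciled lesion rules.
- **Other controls.** Weight, glucose, calibration time, injection time, residual dose and uptake time are all specified. The liver check may be meant only as a backstop for gross errors.
- **External guidance.** Appendix B refers to published guidelines for NCI-sponsored studies and to further parameters on the ACRIN site. These may fix some of this; they could not be checked here.
- **Field of view.** The text states "The axial field of view of the CT scan for attenuation correction will range from the mid thighs to the base of the skull". A reader might infer that this too creates false responses. It does not: a lesion outside the field may go unmeasured, but the limit produces no fall in a lesion that is inside it.

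**Conclusion.** The point holds as a measurement-consistency gap. Appendix B permits a change of ROI diameter that, in small lesions, can be as large as the effect being measured, and this undercuts the reproducibility reasoning in Section 2.3 for lesions of about 1.5 cm or less. By 3 cm the effect has vanished. The sizes depend on the assumed resolution and contrast. The liver threshold of 4.0 is plain arithmetic; the statement that errors of up to 67% (liver SUV 1.5) or 33% (liver SUV 3.0) pass depends on the assumed liver range. The consequence is noise or bias in the change-in-SUV analyses, whether judged by the 25% rule or by the ROC cut-off. It is worth correcting because correction costs little, not because any main conclusion of the trial is at risk.

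**What to change.** In Appendix B:

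1. Choose the PET lesion once, at baseline, under a single rule that reconciles Image Analysis with Image Interpretation. Use that lesion and the same ROI diameter at baseline, day 28 and day 56.
2. Name the three-ROI mean as the SUV for Section 12.4, with the maximum SUV as supportive.
3. Replace the absolute 1.0 trigger with a relative one, for example a change of more than 20% of the baseline liver value. The 20% echoes the test-retest figure in Section 2.3 and is a choice, since the documents give no liver reproducibility. Report the tumour-to-liver ratio as a sensitivity check; liver SUV is already recorded.

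No new scan is needed, and ROIs can be redrawn on stored images, including those of patients already treated. The cost is some re-reading and more SUV calculations sent for re-checking. If the cited external guidance already fixes any of these items, stating so in Appendix B would be enough for that item.
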